### ***Quality Assurance***

Accuracy and completeness of the data collected will be ensured by weekly review. The REDCap system does not accept outliers, illogical response patterns, etc. The PI and research assistants will have weekly meetings to discuss any qualitative comments received during data collection and any problems in data collection. The PI will examine the database for potential irregularities monthly. Initial data analyses will examine distributions of variable scores and comparability of baseline characteristics across conditions in case analyses need to be adjusted for these. Confidentiality procedures are outlined above.

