Statistical Analysis Plan

Sample Size and Power Analysis

Using a chi-square testing framework and a significance level of 0.05 and assuming two-sided hypothesis testing, both primary and secondary outcomes included a large enough sample size to detect differences between groups. Our a priori group sample sizes (usual care: n=191; LTWP: n=224) provided 80% power to detect between-group absolute differences in proportions ranging from 6% to 12% in the primary study outcomes (for example, screened: 65.2% [usual care] versus 77.7% [LTWP]; screened positive: 21.7% versus 34.2%, respectively; referred: 12.5% versus 23.1%, respectively; and attended treatment: 2.1% versus 8.3%, respectively). Our group sample sizes among participants completing a screen (usual care: n=63; LTWP: n=221) provided 80% power to detect between-group absolute differences in proportions ranging from 11% to 18% in the secondary study outcomes (for example, screened positive: 17.5% [usual care] versus 35.4% [LTWP]; referred: 3.2% versus 15.3%, respectively; and attended treatment: 1.6% versus 12.3%, respectively). The usual care rates used in these calculations were based on data published from earlier work on the LTWP program.

Data Analysis

We will assess the adequacy of randomization by comparing LTWP versus usual care (UC) on demographic, obstetric, and psychiatric baseline characteristics, using t-tests or Wilcoxon rank sum tests for continuous variables and chi-square tests or Fisher's exact tests for categorical variables, respectively. Descriptive statistics will be calculated for each screening method (LTWP versus usual care), including counts and percentages for participants who were screened, screened positive, referred to treatment, and attended treatment. Unadjusted differences in outcomes between people assigned to LTWP versus UC will be calculated using chi-square tests because all study outcomes are dichotomous. Relative risk (RR) ratios will be estimated and reported along with their 95% confidence intervals. All hypothesis tests will be two-sided with a type 1 error set at 0.05, and all analyses will be performed using SAS statistical software, version 9.4 (Cary, NC).

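### Baseline significance tests cannot show whether randomisation worked, and the two documents leave open whether the outcome analysis is adjusted, and for what

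*SAP*

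**What the plan says.** **SAP, Data Analysis.** The purpose of the baseline comparison is stated as: "We will assess the adequacy of randomization by comparing LTWP versus usual care (UC) on demographic, obstetric, and psychiatric baseline characteristics". The method given for it is significance testing, namely "using t-tests or Wilcoxon rank sum tests for continuous variables and chi-square tests or Fisher's exact tests for categorical variables". On outcomes: "Unadjusted differences in outcomes between people assigned to LTWP versus UC will be calculated using chi-square tests because all study outcomes are dichotomous". The effect measure is given separately: "Relative risk (RR) ratios will be estimated and reported along with their 95% confidence intervals". On error control: "All hypothesis tests will be two-sided with a type 1 error set at 0.05". The section names no covariate, no stratified or regression analysis, and no link from the baseline tests to the outcome analysis. It also does not say that adjustment is excluded.

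**Protocol, 12.0, Quality Assurance.** Initial analyses will look at score distributions and "comparability of baseline characteristics across conditions in case analyses need to be adjusted for these". No test, threshold, covariate list or model is given.

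**Protocol, 8.0 Recruitment Methods.** ICD codes are the urn stratification factor at randomisation. The SAP does not mention this factor.

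**Protocol, 10.0 Study Design / Methods.** Allocation is 2:1 (LTW to TAU) in both aims and reverses to 1:2 within Specific Aim 2, from approval of amendment 12.

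**The concern.** There are two linked problems.

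First, the baseline tests are asked a question they cannot answer. If allocation was properly random, differences in pre-randomisation characteristics are due to chance, and a p-value tests something already known. It also says nothing about whether an imbalance matters: a strongly prognostic variable can be unbalanced without reaching p<0.05, and an irrelevant one can reach it. In this trial a systematic difference could also arise from the change of allocation ratio rather than from faulty randomisation.

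Second, the protocol defers the adjustment decision until the arms have been compared, and the SAP neither repeats nor withdraws that option. At stake is whether the headline relative risk and p-value come from one analysis named in advance or from a choice between two that both look planned.

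**Working it through.** **1. The plan's own figure.** The SAP gives the group sizes for the primary outcomes as "usual care: n=191; LTWP: n=224". It then states that numbers of this size "provided 80% power to detect between-group absolute differences in proportions ranging from 6% to 12% in the primary study outcomes". The formula is the two-sided pooled-variance chi-square at 0.05 without continuity correction:

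power = Φ{ [ |p2 − p1| − 1.96·√( p̄(1−p̄)(1/n1 + 1/n2) ) ] / √( p1(1−p1)/n1 + p2(1−p2)/n2 ) }

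For attendance (2.1% v 8.3%), p̄ = (191×0.021 + 224×0.083)/415 = 0.0545, the numerator is 0.062 − 1.96×0.02235 = 0.0182, the denominator is 0.02115, and Φ(0.86) = 80.5%.

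| Primary outcome | Usual care v LTWP | Power |
|---|---|---|
| Screened | 65.2% v 77.7% | 80.6% |
| Screened positive | 21.7% v 34.2% | 80.8% |
| Referred | 12.5% v 23.1% | 80.3% |
| Attended treatment | 2.1% v 8.3% | 80.5% |

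The secondary outcomes (63 v 221) give 80.2%, 80.4% and 80.4%. The stated 80% reproduces, and it is the power of the unadjusted test.

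**2. Chance findings at baseline.** With sound randomisation and k independent tests at 0.05, P(at least one p<0.05) = 1 − 0.95^k. The SAP does not count its variables, so k is an assumption.

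| k | 5 | 10 | 15 | 20 |
|---|---|---|---|---|
| P(at least one) | 23% | 40% | 54% | 64% |

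Correlated baseline scales would lower these figures.

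**3. The allocation switch.** The SAP total, 191 + 224 = 415, exceeds the 350 planned for Aim 2 (Protocol 6.0). This suggests that participants are pooled across aims, though neither document says so. As an illustration, suppose all 415 are pooled and the ratios held exactly, with x enrolled at 2:1 and y at 1:2:

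- x + y = 415 and (2/3)x + (1/3)y = 224, so 2x + y = 672, x = 257 and y = 158.
- LTWP from the earlier period: (2/3)×257 = 171.3, and 171.3/224 = 76%.
- Usual care from the earlier period: (1/3)×257 = 85.7, and 85.7/191 = 45%.

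Any characteristic that drifted over time would then differ between arms with nothing wrong in the randomisation. A baseline test would report this as a randomisation problem. If the outcome rates also drifted, the unadjusted comparison would absorb part of that drift.

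**4. What leaving the choice open can cost.** A simulation used 191 v 224, no treatment effect, a continuous outcome, and one continuous covariate with an assumed correlation of 0.2, 0.4 or 0.6 with the outcome. It ran 10,000 replicates per setting, so the Monte Carlo standard error is √(0.05×0.95/10,000) = 0.2 points. Type I error at nominal 5%:

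| Strategy | 0.2 | 0.4 | 0.6 |
|---|---|---|---|
| Always unadjusted | 4.7% | 4.8% | 5.3% |
| Always adjusted | 4.8% | 4.7% | 5.5% |
| Adjusted only if baseline p<0.05 | 4.6% | 4.4% | 4.4% |
| Smaller of the two p-values | 5.7% | 6.4% | 8.2% |

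Only the free choice inflates the error. The trial's outcomes are dichotomous and its covariates unnamed, so these figures show direction and not the size here.

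**5. Room for covariates.** Expected attenders at the planning rates are 0.021×191 = 4.0 in usual care and 0.083×224 = 18.6 under LTWP.

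**The case against.** The strongest reply is that the SAP governs. It names an unadjusted chi-square test and a relative risk, so the outcome analysis is already fixed, and a sentence in a quality-assurance paragraph does not override it. Dropping baseline p-values would then be a reporting improvement only. This has force, but neither document states which takes precedence, and the SAP does not withdraw the protocol's option. An adjusted result could still be defended by pointing to the protocol.

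Three stronger readings are tempting, and the documents do not support them.

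- *The SAP has an unadjusted-only rule that the protocol contradicts.* It has no such rule. It describes unadjusted tests and is silent on adjustment. This is an unreconciled gap, not an explicit contradiction.
- *A significant baseline test triggers adjustment, so more than half of such trials would adjust by chance.* The protocol names no test or threshold, and the SAP does not connect its baseline tests to the outcomes. The 54% to 64% is the chance of any baseline p<0.05 with 15 to 20 independent variables. It is not a probability of adjustment.
- *Conditional adjustment by itself inflates the type I error.* In the simulation a strict pre-test rule on one covariate was slightly conservative (4.4% to 4.6%).

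It is also fair to object that adjustment has a price: so few attenders cannot carry a long covariate list, and the stated power is that of the unadjusted test. That stands, and it limits the remedy.

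**Conclusion.** The point holds in a limited form and is worth correcting. The baseline tests cannot establish whether randomisation worked. If the two allocation periods are pooled, they could signal a failure that did not happen. On adjustment, the two documents together permit two different primary results, and the urn factor used at randomisation appears in neither description of the analysis.

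The harm depends on how the choice is made. There is no inflation if one analysis is applied regardless of the data. The inflation was 0.7 to 3.2 points above the nominal 5% in the illustrative simulation if the more favourable result may be selected. The size in this trial is not known. The period imbalance of 76% v 45% rests on full pooling and exact ratios, neither of which the documents confirm. The SAP's power figures are sound and are not in question.

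**What to change.** 1. **SAP, Data Analysis:** replace the baseline tests with a descriptive table by arm, without p-values.
2. **Protocol, 12.0, Quality Assurance:** delete the words that make adjustment conditional on baseline comparability.
3. **Both documents:** state one primary analysis, applied whatever the baseline table shows. One suitable form is a Mantel-Haenszel relative risk and test stratified by ICD urn group and, if periods are pooled, by allocation period. Keep the unadjusted chi-square and relative risk as a supporting analysis. Pregnant versus postpartum at enrolment is optional. Use only factors known before randomisation.
4. **SAP:** say whether participants from before and after the allocation switch are pooled, and that the 80% power refers to the unadjusted test.

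**Cost:** a few sentences in each document and slightly more analysis work. The adjustment set must stay small. If the urn has two levels (the number is not stated) and there are two periods, the 4 expected usual-care attenders average one per stratum. Mantel-Haenszel methods can work with strata that sparse, but further factors would leave little information in each. The power of the stratified analysis cannot be computed from the documents, because they give no stratum sizes or stratum-specific rates.

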## **6.0 Number of Subjects**

A total of 450 participants will be randomized in Specific Aim 1 (n=100) and Specific Aim 2 (n=350). To randomize 450 participants we will need to approach about 1,500 participants in order to get to 450 total participants.

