## **10.0 Study Design / Methods**

Specific aim 1: A two arm pilot RCT (N=100) with 2:1 allocation will examine feasibility and preliminary efficacy of LTW, compared to TAU. Specific aim 2: A RCT (N=350) with 2:1 allocation will examine effectiveness of LTW, compared to TAU. As of the approval of amendment #12 the allocation will switch to 1(LTW):2(TAU) for specific aim 2. Recruitment will primarily occur proactively and remotely via the EHR. We will conduct a weekly EHR search via a recruitment report for all new pregnant and postpartum patients in the past week. The report will include mrn, age, race, ethnicity, date of prenatal care visit, date of postpartum visit, delivery date, ob/gyn provider name, MyChart account (Yes/No), cell phone number, email address and current ICD-9 or 10 diagnoses. Any patients who have not opted out of being contacted for research will be contacted and invited to participate. The study team will not cold-contact any patients who have chosen to opt-out of receiving contact about research or who have met the maximum number of contact attempts at the time of recruitment. If the potential participant has not opted out of being contacted, or the potential participant's provider has agreed to have the study team contact their patient, a phone call will be made or message will be sent via text, email or MyChart message to the potential participant inviting them to take part in the study. This invitation will include clear opt out procedures should the patient not wish to be contacted in the future for the purpose of this study. If interested, participants will complete a screening online via REDCap to determine study eligibility (see above for inclusion criteria). After completing preliminary determination of eligibility, if eligible and interested in participating in the study, participants will be scheduled for a time to complete informed consent (see 9.0 Consent Process).

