\*\*Only participants in specific aim 2 complete the GAD-7, CSSRS and TLFB

\*\*\*Only participants assigned to LTW will complete the usability scale

+ As of the approval of amendment 10 newly enrolled participants will not complete CSSRS and TLFB. Participants consented prior to the approval of amendment 10 will complete CSSRS and TLFB at baseline.

Specific aim 3: We will gather healthcare utilization data on our study participants who have Medicaid insurance. The MUSC study team will extract the maternal Medicaid IDs from our study participants with Medicaid insurance from the EHR. We will share a list of these maternal Medicaid IDs with Medicaid, and they will return data related to maternal and newborn diagnosis codes, health care utilization and costs for these participants i.e., prenatal care visits, postpartum care visits, hospitalizations and ED visits during pregnancy and the postpartum year. The MUSC study team will send the maternal Medicaid ID's of study participants to Medicaid in a password protected spreadsheet. Medicaid will send the MUSC study team a password protected spreadsheet of data. The spreadsheet of data Medicaid will send back to MUSC will be coded since

it will contain the Medicaid ID's of participants.

The Medicaid ID is the only link to subjects in the study. The document linking Medicaid ID's and our study participants will be stored on a University secure network drive or in MUSC BOX. The linking document will be stored separately from the study data and only trained study personnel will have access to the linking document.

Study data will be stored on a University secure network drive or in MUSC BOX. The spreadsheet of data that Medicaid will send the MUSC study team will be password protected. Only trained study personnel will have access to the password protected data spreadsheet.

The MUSC study team will have access to the Medicaid ID's as well as Medicaid.

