### **13.0 Risks to Subjects**

This is considered a minimal risk study. Minimal risk means the probability and magnitude of harm or discomfort anticipated in the research are not greater in and of themselves other than those ordinarily encountered in daily life or during performance of routine physical or psychological examinations or tests. The LTW screening tool is the same tool that is used in clinical practice, the only difference is in its delivery. The potential risks in this study include those related to: a) confidentiality; b) frustration; and c) emotional distress.

- a) Confidentiality:** Participants will be made aware of limits to confidentiality at the beginning of screening and when reviewing study procedures/during informed consent which include report of suicidal or homicidal intent or report of abuse or neglect. If the participant reports substance use during pregnancy or suicidal or homicidal intent or abuse/neglect, [name] will take appropriate action by completing a psychiatric assessment and facilitating appropriate treatment. Additional appropriate actions as outlined by the MUSC IRB, NIH, and the State of South Carolina, may also include contacting the department of social services, authorities and/or pursuing involuntary commitment at a mental health or substance use disorder treatment facility. If participants present no imminent danger but also need more extensive treatment of mental health or substance use concerns, appropriate care will be facilitated.
- b) Frustration:** Participants may become frustrated while completing study assessments. Participants will be informed that they may refuse to answer any question(s) that they do not wish to answer and that they may discontinue study participation at any time.
- c) Emotional Distress:** Participants will be asked questions that may be sensitive in nature. Participants may find the questions distressing or find the questions make them feel uncomfortable. Participants will be informed that they may refuse to answer any question(s) that they do not wish to answer and that they may discontinue study participation at any time.

Since patients will all currently be receiving prenatal care or will be currently postpartum, there are no additional risks associated with participation in this study.

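### Allocation reverses from 2:1 to 1:2 during the trial, but the SAP compares pooled arms with an unadjusted chi-square, so part of any drift over time is counted as treatment effect

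*SAP*

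**What the plan says.** Protocol Section 10.0 sets 2:1 allocation for the pilot (Aim 1) and for the main trial (Aim 2). It then adds: "As of the approval of amendment #12 the allocation will switch to 1(LTW):2(TAU) for specific aim 2". Section 6.0 plans 450 randomised women, 100 in Aim 1 and 350 in Aim 2.

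The SAP gives one pair of arm sizes: "Our a priori group sample sizes (usual care: n=191; LTWP: n=224) provided 80% power to detect between-group absolute differences in proportions". Its Data Analysis section specifies one comparison: "Unadjusted differences in outcomes between people assigned to LTWP versus UC will be calculated using chi-square tests because all study outcomes are dichotomous". Relative risks with 95% confidence intervals are to be reported, with no adjustment named, and "All hypothesis tests will be two-sided with a type 1 error set at 0.05".

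Neither document names allocation period, calendar time or aim as a stratum or covariate. The only mention of adjustment is in protocol Section 12.0 (Quality Assurance), where initial analyses look at "comparability of baseline characteristics across conditions in case analyses need to be adjusted for these".

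**The concern.** Randomisation makes the arms comparable within each allocation period. It does not do so once a 2:1 period and a 1:2 period are added together: LTW women then come mostly from the earlier period and usual-care women mostly from the later one. If screening, referral or attendance rates differ between the periods for any reason, the crude comparison mixes that change with the treatment effect. Falling rates favour LTW and can produce a false positive. Rising rates count against LTW and can hide a real benefit.

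The protocol records at least one procedural change over the trial. A note to the Section 10.0 assessment table says "As of the approval of amendment 10 newly enrolled participants will not complete CSSRS and TLFB". Section 13.0 says that, when a woman reports suicidal intent or substance use in pregnancy, the study "will take appropriate action by completing a psychiatric assessment and facilitating appropriate treatment". That response lies on the path to referral and attendance. By the amendment numbering, no woman randomised at 1:2 completed those two instruments. Whether this moved any outcome is unknown.

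**Working it through.** **Inputs.** From the SAP: arms of 224 (LTW) and 191 (usual care), two-sided 5% test, and usual-care versus LTW rates of 65.2% v 77.7% (screened), 21.7% v 34.2% (screened positive), 12.5% v 23.1% (referred) and 2.1% v 8.3% (attended). From protocol Section 10.0: 2:1, read as LTW:TAU, then 1:2.

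**1. The SAP's power reproduces.** The two-proportion normal approximation without continuity correction gives 80.6%, 80.8%, 80.3% and 80.5% for the four outcomes. The stated 80% is right for an unstratified comparison.

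**2. The arms mix both periods.** The total is 224 + 191 = 415, more than Aim 2's 350. The ratio is 224/191 = 1.17. Under simple allocation of 415 women the SD of the LTW count is √(415 × 2/9) = 9.60. At 2:1 the expected count is 276.7, so 224 is 5.5 SD too low. At 1:2 it is 138.3, so 224 is 8.9 SD too high.

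**3. Implied split (assumption: realised allocation equals the stated ratios).** With *x* women randomised at 2:1, (2/3)*x* + (1/3)(415 − *x*) = 224 gives *x* = 257, leaving 158 at 1:2.

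| | 2:1 period | 1:2 period | Share from 2:1 period |
|---|---|---|---|
| LTW (224) | 171 | 53 | 76% |
| Usual care (191) | 86 | 105 | 45% |

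**4. Leak.** With no treatment effect, the expected crude difference equals the drift times 171/224 − 86/191 = 0.313. For a general fraction *f* randomised before the switch, the leak is 2*f*/(1 + *f*) − *f*/(2 − *f*): 26% at *f* = 0.25, 33% at 0.50 and 26% at 0.75. If all of Aim 1 is included, *f* is at least 100/415 = 24%.

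**5. Type I error, worked example.** Let the rate be 70% in the first period and 60% in the second, in both arms.
- LTW: (171 × 0.70 + 53 × 0.60)/224 = 67.6%
- Usual care: (86 × 0.70 + 105 × 0.60)/191 = 64.5%
- False difference: 3.13 points
- SE: √[0.662 × 0.338 × (1/224 + 1/191)] = 4.66 points, a shift of 0.672 SE
- Rejection probability: P(Z > 1.288) + P(Z < −2.632) = 9.9% + 0.4% = 10.3%

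Simulation (400,000 trials per scenario, no treatment effect in either period) agrees:

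| Rate, first to second period | Crude type I error |
|---|---|
| No drift | 5.0% |
| 70% to 67% | 5.5% |
| 70% to 65% | 6.4% |
| 70% to 60% | 10.3% |
| 75% to 55% | 27% |
| 12% to 9% | 5.9% |
| 15% to 10% | 7.2% |
| 5% to 3% | 5.6% |
| 8% to 2% | 12.4% (favours LTW) |
| 2% to 8% | 14.9% (against LTW) |

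The Cochran-Mantel-Haenszel (CMH) test in two strata stays at 4.7-5.1% throughout.

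**6. Rising rates with a real benefit.** If LTW adds 12.5 points to screening in both periods while usual care rises from 60% to 70%, power is 55% crude and 76% stratified. If LTW adds 6.2 points to attendance while usual care rises from 1% to 5%, it is 59% and 75%.

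**7. Price of stratifying when there is no drift.** The effective information is 224 × 191/415 = 103.1 pooled, against 171.3 × 85.7/257 + 52.7 × 105.3/158 = 92.2 stratified, a ratio of 0.89. The SE rises by about 6%. Simulated power, crude v CMH: screened 80.9% v 76.3%, screened positive 81.0% v 76.6%, referred 80.8% v 76.4%, attended 83.5% v 78.8%.

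**The case against.** The strongest reply is that no drift in any outcome is documented and that the large error rates need large drifts. A 27% error takes a 20-point fall; 12.4% and 14.9% take a four-fold change in attendance, about as large as the whole planned effect. At drifts of about 3 points the error is only 5.5-5.9%. This stands as a limit on the size of the problem, not on its existence.

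Second, the dropped instruments are weak evidence of drift. They were completed only in Aim 2 and stopped at amendment 10. On the split above, at most 257 − 100 = 157 women completed them, about 46.7% of LTW and 27.4% of usual care, so this channel leaks at most about 19%, not 31%. Section 13.0 names neither instrument, and the NIDA-Modified Assist stays at baseline. This also stands: the channel is plausible, not shown.

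Third, the SAP counts 63 usual-care and 221 LTW women completing a screen. Read as subsets of 191 and 224, that is 33% v 98.7%, a gap of about 66 points that no drift could explain with a leak of at most one third. That reading would protect the screening result. It does not protect referral or attendance, and attendance is Aim 2's primary outcome (Section 4.0).

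Fourth, baseline adjustment might catch drift that works through measured case-mix. But that adjustment is conditional, does not name period, and is contradicted by the SAP's unadjusted test.

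Finally, pooling is inferred: the SAP never says so, and 415 matches none of 100, 350 or 450. Even so, a ratio of 1.17 cannot plausibly come from either allocation alone.

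**Conclusion.** The concern holds. An unadjusted test on arms that combine a 2:1 period and a 1:2 period is valid only if outcome rates did not change between them, and the plan gives no ground for assuming that. Confidence in the mechanism is high. The size is illustrative, because the documents give no switch date, counts by period or rates by period. Assuming that realised allocation matched the stated ratios, about 31% of any drift enters the treatment comparison (26-33% if a quarter to three quarters of women precede the switch). A 5-point fall from 70% gives 6.4% type I error and a 10-point fall gives 10.3%. Drifts of about 3 points or less in screening matter little, and with no drift there is no bias. Attendance is the most exposed: a 5-point drift would leak about 1.6 points into a planned 6.2-point difference. The point affects the validity of the primary comparison and should be settled before the data are analysed.

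**What to change.** Make the primary analysis a CMH test with a Mantel-Haenszel relative risk and 95% CI in two strata: all women randomised at 2:1 (Aim 1 plus Aim 2 before amendment 12) and all women randomised at 1:2. Report the switch date, the counts by arm and the results within each period. Keep the crude chi-square and relative risk as a sensitivity analysis. Choosing this in advance also prevents a choice between the two answers once results are seen.

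For attendance, add an exact stratified p-value. About 4 usual-care events are expected (0.021 × 191), and the chance of none is 0.979^86 = 16% in the first period, 0.979^105 = 11% in the second and 1.7% in both. In simulation at these rates the CMH test and the Mantel-Haenszel interval still behaved acceptably: type I error 4.75% with 2.1% in both arms, interval coverage 96.8% at 2.1% v 8.3%.

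The cost is SAP wording, a before/after amendment 12 flag for each woman, and a restated power paragraph. The documents do not say that the flag is stored, but randomisation is a scheduled baseline item in Section 10.0. Power at the SAP's own differences becomes 76-79%, so the stated 80% no longer holds. No extra enrolment is asked for: the precision given up came from comparing women across periods, which the randomisation does not support.
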